8.2 Sample size estimate

We anticipate that identification of at least 700 individuals in the intervention group and control group should be sufficient to detect an average change of 0.5% in A1c, assuming an $\alpha=0.05$, $1-\beta=0.80$, A1c standard deviation=1.9, and a verbal informed consent rate of 45%, including clustering and non-differential loss-to-follow up between the study groups (Table 5). With this sample size, we should also have the ability to detect differences in the adherence outcomes (Table 6).

Based on feasibility information from Horizon, we anticipate that of the 315 patients in the intervention group who are likely to be reached by pharmacists (45%), at least 236 will have usable follow-up data. This proportion of reached patients has been observed in prior, pilot studies that have used a similar approach.²⁵ In order to observe an overall A1c difference of 0.5% in the study population, these contacted patients must have a underlying mean A1c change of ~0.49% (Figure 3). This difference is in line with what clinical guidelines consider to be a clinically meaningful difference in glycaemic control. This A1c difference has been observed in prior work with clinical pharmacists.⁸ This sample size would also provide enough patients for the predictive analytics work, given the relative non-rare nature of the study outcomes (glycemic control and medication adherence).

Table 5. Justification: A1c power calculation parameters and ranges

Range of parameters: input ranges	A1c difference: 0.5% Sample size (N range)/group
A1c SD: 1.9-->N1	228
Intra-cluster correlation (N ₂ =N ₁ * 1.03)	235
Loss-to-follow-up (LTF): 15-30%	(best case: 276, worst case: 335)

Date

(N ₃ =N ₂ /[1-rate])	
Pharmacist contact rate: 35-50% (N ₄ =N ₃ /rate)	(best case: 552, worst case: 959)
Total	45% reach rate and 25% LTF: 696 patients/arm

Power (1-β): 0.80; Alpha (α): 0.05

Explanation of study parameters – Primary outcome (A1c)

- 1) Standard deviation of A1c: ranges between 1.0 and 2.0, depending on study length and average baseline A1c values. The most commonly cited value is 1.9, assuming equal variances between the groups. This would be non-differential between study groups.
- 2) Intra-cluster correlation: Other studies have also incorporated intra-cluster correlation (ICC) within PCP clinics (~0.03 for small pilot studies). This would be non-differential between study groups.

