1.3 Number of subjects

In total, 1,400 subjects were randomized in a 1:1 ratio to the intervention or control group. Our study was designed to be sufficiently powered to detect small but clinically meaningful changes in the primary outcome of HbA1c change.

We considered the following assumptions in the power calculations. Assuming that 30% of study subjects in the intervention arm agree to participate in the intervention, we randomized 700 individuals

to each of the intervention and control groups in order to achieve 80% power to detect an average change in HbA1c of 0.5% between the intervention and control groups at an alpha threshold of 0.05 with a HbA1c standard deviation=1.9 (the most commonly cited value in the literature for HbA1c), accounting for 25% rate of loss-to-follow-up.^{1,2} We used Proc Power in SAS 9.4 (Cary, NC) using a t-test and adjusted the sample size to account for the reach rate. Because patients may change insurance, in particular at the end of the calendar year, we accounted for a rate of non-differential loss-to-follow-up of 25% rate. There may also be patients who do not have follow-up HbA1cs, despite restricting to patients whose providers have at-risk contracts with Horizon Blue Cross Blue Shield. As described later in Section 3, we will use multiple imputation methods to account for patients with no follow-up HbA1c values. In addition, this proportion of patients who agree to participate in this intervention has been observed in prior studies that have used a similar approach.²⁵ Finally, the proposed difference of HbA1c of 0.5% is the level that clinical guidelines consider to be a clinically meaningful difference in glycemic control. This HbA1c difference has also been observed in prior work with clinical pharmacists.⁸ Because the primary outcome is HbA1c change, we expect to see clinically meaningful differences in these levels within the 11 to 12-month follow-up period.^{3,4}

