For secondary outcomes, with this sample size, we will also have the power to detect at least a 4% absolute difference in adherence (i.e., mean PDC levels) between the intervention and control groups, assuming baseline rates of adherence of 50%. We used Proc Power in SAS 9.4 (Cary, NC) using a chi-square test and adjusted the sample size to account for the reach rate. These differences in adherence have been observed as meaningful in prior research, and the baseline rate of adherence is based on prior research in this field.⁵⁻⁷ In addition, prescription claims will be captured on all patients included in the study by definition for inclusion, enabling the calculation of adherence in the follow-up period until loss of continuous eligibility. Therefore, there is no substantial lost-to-follow up expected for this outcome.

Finally, for the secondary objective (Aim 2), this sample size would also provide enough patients for the predictive modelling, given the relative non-rare nature of the study outcomes (glycemic control and medication adherence) and number of predictors considered per number of patients in the study.⁸

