4.2 Analysis methods

4.2.1 Primary objective (Effectiveness of intervention):

Baseline characteristics:

We will measure key baseline characteristics in the 12-months prior to randomization in the pharmacy and medical claims data and enrolment files. These characteristics will include sociodemographic characteristics, such as age and sex, which will be measured in the enrolment files. We will also measure baseline clinical characteristics such as the presence of coronary artery disease, chronic obstructive pulmonary disease, asthma, hypertension, hyperlipidemia, congestive heart failure, depression, liver disease, chronic kidney disease, osteoporosis and prior macrovascular complications. These will be measured in medical claims files using ICD-10 codes. We will also measure the type of oral glucose-lowering agent used in the baseline period (e.g., medical class), average PDC at baseline, and whether or not the medication is branded. We will also measure patients' latest copayments for oral glucose-lowering agents in the baseline period. Finally, we will also measure baseline healthcare resource utilization variables as characteristics including the number of days hospitalized and the number of physician office visits.

We will report, in tabular format, the means and frequencies of baseline characteristics prior to assignment separately for patients in the intervention and control groups and compare these values using t-tests, chi-square tests, and their non-parametric analogues, as appropriate. We will provide absolute standardized differences between the two treatment groups.

Primary analyses:

Primary outcome (change in HbA1c): In the primary analysis, the primary outcome, mean change in glycemic control, will be compared using generalized estimating equations with an identity link function (as a continuous variable) and normally distributed errors within the imputed full analysis set, as described above. Data will be presented as the unadjusted absolute difference in the change in HbA1c between the groups along with 95% confidence intervals.

Secondary outcome (proportion achieving glycemic control)

1) *Proportion of patients achieving optimal glycemic control* (defined by HbA1c < 8): This outcome will be compared using generalized estimating equations with a logit link and binary distributed errors. Data will be presented as the unadjusted odds ratio for optimal glycemic control between the groups along with 95% confidence intervals.

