For each outcome (e.g., $HbA1c < 8\%$ and $PDC \geq 0.80$), we will first estimate a model that includes only demographic and clinical characteristics. We will then estimate additional models that include these predictors as well as baseline medication adherence. Receipt of the pharmacist intervention will be tested using an interaction term so the logistic regression will provide estimates on all patients and not just those receiving the intervention. We will also repeat the analyses among the subgroup of intervention patients who had at least 1 telephonic encounter with a pharmacist to examine which set of characteristics are most predictive of the response to the intervention. Model estimation will be repeated among relevant patient subgroups (e.g., gender, age) to see if there are any differences in predictive ability.

Models among each of the control and intervention groups will be predicted using both logistic regression and generalized boosting regression, a data mining technique that generates a prediction model through building many regression trees with the potential for many interactions among the predictors.¹⁸ Through these many regression trees, the model can incorporate a number of non-linear associations between the predictors and the outcomes; this approach is considered to be one of the best prediction approaches. Alternative methods of clustering patients who are most likely to respond will also be explored, including machine learning to develop models algorithmically, to partition patients into clusters that have a similar likelihood of experiencing the clinical outcomes.¹⁹

Model accuracy:

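### The SAP's claim that the sample is large enough for Aim 2 is made for the whole study; the contacted-only refit has about 158 to 236 patients for 13 to 25 terms, with no shrinkage planned, and is likely to be heavily overfitted

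*SAP*

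**What the plan says.** SAP 1.3 closes with the statement that "this sample size would also provide enough patients for the predictive modelling". It gives two reasons: the outcomes are not rare, and the "number of predictors considered per number of patients in the study". It states no predictor count, expected R-square, shrinkage target or number of patients for any single model.

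SAP 4.2.2 then describes a family of models for HbA1c below 8% and PDC of at least 0.80. The first uses demographic and clinical characteristics only. Later ones add baseline adherence. They are fitted by logistic regression and by boosting, in the whole sample with an intervention interaction and within each arm. They are repeated in subgroups such as sex and age. There is also a refit in contacted patients: "We will also repeat the analyses among the subgroup of intervention patients who had at least 1 telephonic encounter with a pharmacist". Its stated purpose is to find the characteristics that best predict response to the intervention.

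The candidate predictors are in SAP 4.2.1. They include age, sex and the "presence of coronary artery disease, chronic obstructive pulmonary disease, asthma, hypertension, hyperlipidemia, congestive heart failure, depression, liver disease, chronic kidney disease, osteoporosis", plus prior macrovascular complications, drug class, baseline PDC, brand status, copayment, hospital days and office visits. Neither 4.2.1 nor 4.2.2 mentions a penalty or other shrinkage for the regression models. Accuracy is judged by C-statistics and R-squares under 10-fold cross-validation, and the Protocol (2.2) names both as outcome measures of the secondary objective.

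**The concern.** A ratio of predictors to patients that is comfortable in 1,400 people says little about a model fitted to a fraction of one arm. The contacted-only refit is the smallest of the main models, yet it is the one meant to show which patients respond.

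Cross-validation measures overfitting; it does not remove it. A low or negative cross-validated R-square from a small unpenalised model could mean that response is hard to predict, or only that too many coefficients were estimated from too few patients. The planned logistic results could not separate the two. The Protocol (8.1) intends these results to inform payers and providers about likely responders, so the distinction matters, although the trial's primary conclusion is untouched.

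**Working it through.** **The plan's own count.** The Protocol (8.2) assumes 45% reach and 25% loss: 700 × 0.45 × 0.75 = 236.25, which reproduces its statement that "at least 236 will have usable follow-up data".

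**The count under the SAP.** Inputs from SAP 1.3: "1,400 subjects were randomized in a 1:1 ratio", so 700 per arm; "Assuming that 30% of study subjects in the intervention arm agree to participate in the intervention"; and "accounting for 25% rate of loss-to-follow-up".
- Contacted: 700 × 0.30 = 210. This applies to PDC, for which SAP 3.3 expects no missing data, and to HbA1c if imputation extends to Aim 2, which the SAP does not say.
- Contacted with observed HbA1c: 210 × 0.75 = 157.5, about 158.
- Whole sample with observed HbA1c: 1,400 × 0.75 = 1,050.

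**Terms.**
- First model: 2 demographic + 11 clinical = 13.
- All of 4.2.1 with drug class as one term: 13 + 1 + PDC 1 + brand 1 + copayment 1 + utilisation 2 = 19.
- With the seven oral classes in Protocol Table 2 as separate terms: 13 + 7 + 5 = 25.
- Whole sample with every predictor interacting with arm: 25 + 1 + 25 = 51.

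**Events per term.** The documents give no outcome frequency; 30% to 50% is assumed.
- 158 patients: 47 to 79 events, so 1.9 to 3.2 per term with 25 terms and 3.6 to 6.1 with 13.

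**Patients needed for expected shrinkage of 0.9.** N = p / [(S − 1) ln(1 − R²cs/S)], with S = 0.9 and R²cs the Nagelkerke R-square times its maximum (0.75 at 50% events, 0.705 at 30%).
- True R-square 0.40, 50% events: R²cs = 0.30, ln(1 − 0.30/0.9) = −0.405. So N = 25/0.0405 = 617 for 25 terms and 13/0.0405 = 321 for 13. At 30% events: 665 and 346.
- True R-square 0.15, 50% events: R²cs = 0.1125, ln(1 − 0.125) = −0.1335. So N = 1,872 for 25 terms and 974 for 13. At 30% events: about 2,000 and 1,040.

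Even at the generous 0.40, all four results exceed 158, 210 and 236. The 1,050 in the whole sample meets the 13-term requirement at 0.15, though not the 25-term one.

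**Simulation.** Assumptions: independent normal predictors, linear predictor SD 0.7, about 40% events, true C 0.68, true McFadden R-square about 0.075. Each fit was evaluated in 20,000 new patients. Approximate unpenalised R-square:

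| Patients / terms | R-square in new patients |
|---|---|
| 158 / 25 | −0.12 |
| 158 / 19 | −0.05 |
| 158 / 13 | −0.01 |
| 210 / 25 | −0.06 |
| 210 / 13 | +0.02 |
| 236 / 25 | −0.03 |
| 1,050 / 51 | +0.035 |

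The calibration slope is about 0.28 at 158/25 and 0.62 at 1,050/51. With ridge, R-square becomes about +0.02 at 158/25 and 0.048 at 1,050/51. C at 158/25 is about 0.61 against a true 0.68, and ridge barely changes it.

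**Dependence on signal.** On the Nagelkerke scale, with 30% to 50% events, the true R-square above which a typical unpenalised fit turns positive is 0.30 to 0.40 at 158/25, about 0.25 at 158/19 and about 0.15 at 158/13. It is 0.20 to 0.25 at 210/25 and just under 0.20 at 236/25.

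**The case against.** The strongest reply has four parts.

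- **The SAP's claim concerns the whole study.** This stands. The SAP speaks of patients in the study, its analysis set for the secondary objective is all randomised patients (2.1), and the contacted-only fit is a repeat. R-square stays positive in the whole sample even with 51 terms, and 51 is itself a wide reading of a single interaction term. A reader might infer that the SAP's own figures contradict its sufficiency statement. They do not; the statement simply does not cover the refits.

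- **158 and 25 are the extremes.** This stands in part. The sentences in 4.2.2 that name predictors mention demographic, clinical, utilisation and adherence variables, which make 13 to 16 terms; 25 needs everything in 4.2.1 with drug class split. Imputation, or the PDC outcome, gives 210. But 4.2.2 also refers back to the 4.2.1 list, and 210 or 236 patients do not rescue a 25-term model at the assumed signal.

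- **The signal is assumed.** This stands. A reader might infer that the contacted-only model would explain less than nothing in new patients. That needs many terms, few patients and a modest signal together. With a stronger signal (linear predictor SD 1.0), the 13- to 16-term models are all positive, at +0.03 to +0.08.

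- **Cross-validation and boosting are already planned.** They ensure that poor fit is seen. They do not repair the logistic models, and the SAP describes no tuning for the boosting.

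A reader might also infer that the resulting predictor ranking would be mostly noise. Nothing here shows that: discrimination stays above chance, and the accuracy of the ranking was not computed.

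**Conclusion.** The point holds for the contacted-only refit, with weaker force for the sex, age and single-arm refits. About 158 to 236 patients for 13 to 25 unpenalised terms makes heavy overfitting likely, and SAP 1.3 offers no justification at that level. The patient and term counts follow from the documents. The R-square values rest on assumed event rates and signal, with independent normal predictors. At a true C of 0.68 they run from about −0.12 (158/25) to slightly positive (210/13). The cross-validated R-square is therefore a downward-biased guide to how predictable response is, and may be negative; the C-statistic loses some accuracy but stays informative.

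The whole-sample models are adequately supported in that R-square stays positive at this signal, and they gain slightly from shrinkage. The evidence does not require dropping the contacted-only refit or capping it at a handful of predictors. Either is a trade-off the investigators may reasonably decline.

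**What to change.** - In SAP 4.2.2, fit the Aim 2 logistic and linear models with a ridge or elastic-net penalty. Tune the penalty and the boosting settings in an inner loop within each of the 10 folds.
- Report the contacted-only and subgroup refits as exploratory.
- State the terms in each model and whether imputation of HbA1c applies to Aim 2.
- In SAP 1.3, limit the sufficiency statement to the whole-sample models.

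The cost is SAP wording and standard software; no new data are needed. The one real downside is that penalised coefficients carry no ordinary p-values, so the treatment interaction can be tested in a separate unpenalised whole-sample model. Shrinkage should improve R-square and calibration; it should not be expected to raise the C-statistic much.

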2. ANALYSIS SETS

2.1 Definition of analysis sets

Full Analysis Set (Intention to Treat population): The primary and secondary outcomes will be evaluated using intention-to-treat principles among all randomized patients. Within the intervention group, patients who choose to speak with a pharmacist may differ from those who do not, and therefore an intention-to-treat analysis in this randomized study ensures unbiased comparisons to the control group. Therefore, the analysis set for the primary and secondary objectives will be the intention-to-treat population of all patients who meet inclusion and exclusion criteria and are randomized to the trial.

As-treated/per-protocol Analysis Set: We will also explore an “as-treated” analysis that compares patients in the intervention group who received the pharmacist intervention with patients in the usual care group. For this analysis set, the subgroup of patients in the intervention group who agreed to participate in the intervention will be compared against the patients in the control group. This analysis set will not be used for any of the primary analyses, only secondary analyses.

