Seven-hundred patients who meet eligibility criteria will be allocated to the intervention group. These eligibility criteria are described in further detail in Section 3.

The intervention will be delivered by trained and licensed pharmacists from [REDACTED] telephonic disease management services. [REDACTED] has provided patient care services for other patient populations to a number of large insurers, including Horizon BCBSNJ.

The intervention is described in detail below.

Intervention: Shared decision-making/Brief negotiated interviewing

Eligible patients will first be sent an invitation letter. This letter will include a decision aid and pillbox that will prime them for telephonic encounters with pharmacists and will be used to enhance interventional efforts. This decision aid will be developed using principles of decision aid design and be based upon other decision aids that have been previously validated.^{7,8,17,18} An online format for the decision aid will also be made available for patient convenience. Prior to study launch, the study team will solicit direct patient feedback on the decision aid and patient-oriented materials from a cohort of patient volunteers. The study team has established a relationship with local providers who lead regular diabetic support groups and has received their commitment to participate and solicit direct feedback. This patient feedback will be used to refine both the shared decision-making tool and other patient materials in accordance with guidelines on conducting shared-decision making in practice.^{8,17}

To engage patients after the initial mailing and connect them with pharmacists more quickly and directly, an Interactive Voice Response System (IVRS) may also be used. One advantage of an IVRS is that it would provide a triage format for patients to contact the pharmacists directly after receiving the initial mailing. IVRS is frequently used in clinical practices and Horizon BCBSNJ to help manage their patients.

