8.1 Statistical considerations

Aim 1 (Primary Objective):

We have received Horizon Blue Cross Blue Shield Privacy Board approval to receive a HIPAA limited dataset on all patients for the purpose of analysis. The primary analyses will be conducted among all patients identified for the control group and the intervention group on an intention-to-treat basis. This approach will minimize the potential selection bias introduced by comparing only consenting patients to the identified controls, even if patients were carefully matched using observable covariates. Secondary analyses for all outcomes will be conducted among patients who provided informed consent versus the control group.

The primary outcome of interest will be the pre- to post-intervention change in mean HbA1c levels to the end of follow-up. Horizon BCBSNJ receives laboratory information from over 200 patient-centered medical homes and other population health programs and other practices. This laboratory information will be used to measure the change in HbA1c levels at the end of follow-up. Because the primary outcome is HbA1c change, we expect to see clinically meaningful differences in these levels within the 11 to 12-month follow-up period.^{24,25} We will use generalized estimating equations to compare the changes between the two study groups. Any observed imbalance between the groups will be controlled for using multivariable regression.

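### The exploratory as-treated comparison carries potential selection bias of unknown size; a randomisation-based complier estimate reported ahead of it would be a cheap improvement

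*SAP*

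**What the plan says.** SAP 2.1 defines two analysis sets. The full analysis set takes all eligible randomised patients and serves the primary and secondary objectives. The reason given is that "patients who choose to speak with a pharmacist may differ from those who do not". The second set is introduced as exploratory: the subgroup of intervention patients "who agreed to participate in the intervention will be compared against the patients in the control group". Its role is limited: "This analysis set will not be used for any of the primary analyses, only secondary analyses". The section describes this subgroup in two ways, once by receipt of the intervention and once by agreement to take part.

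Protocol 8.1 says that ITT is meant to limit "the potential selection bias introduced by comparing only consenting patients to the identified controls", a bias it expects "even if patients were carefully matched using observable covariates". It then plans that comparison: "Secondary analyses for all outcomes will be conducted among patients who provided informed consent versus the control group".

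SAP 4.2.1 specifies no as-treated model. Its only covariate adjustment is triggered by a standardised difference above 0.1 between study groups. Neither document plans a complier or instrumental-variable estimate.

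The invitation mailing goes to the intervention arm before consent is sought. Protocol 1.2 says of it: "This letter will include a decision aid and pillbox that will prime them" for the pharmacist calls.

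**The concern.** The two sides of the as-treated contrast are not alike. One side is the minority of the intervention arm who agreed: 30% in SAP 1.3, 45% in protocol 8.2. The other is the whole control arm, of whom 55% to 70% would have declined if asked. If people willing to talk to a pharmacist would have improved more anyway, the contrast shows a benefit when the intervention does nothing. If they would have improved less, it hides a real one. Covariate adjustment reaches only what is measured, and the protocol itself says that matching on observables would not be enough.

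The question behind the analysis is a fair one: what does the intervention do for those who take it up? With uptake this low, the ITT effect is heavily diluted and readers will want that answer. At stake is whether the trial reports it from a self-selected contrast or from one that keeps the randomised comparison.

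**Working it through.** **Inputs**
- 700 per arm, SD 1.9, 25% loss to follow-up, two-sided 5% level: SAP 1.3 and 4.1.
- Uptake p: 0.30 (SAP 1.3) or 0.45 (protocol 8.2).
- Controls are not contacted (protocol 3.3) and no contamination is expected (protocol 3), so non-compliance is one-sided.
- d, the difference in HbA1c change between would-be consenters and non-consenters under usual care, is not in the documents. Assumed range: 0.1 to 0.5 points.
- m, the effect of the mailing alone in non-consenters, is not in the documents. Assumed range: 0.02 to 0.10 points.

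**The plan's own figure.** None is given for the as-treated analysis. The shared inputs do reproduce protocol Table 5: 228 × 1.03 = 235, and 235 / 0.75 / 0.45 = 696 per arm.

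**Standard errors.** Evaluable patients: 700 × 0.75 = 525 per arm. Evaluable consenters: 525 × 0.30 = 157.5, or 525 × 0.45 = 236.25.
- As-treated: 1.9 × √(1/157.5 + 1/525) = 0.173 at 30%; 1.9 × √(1/236.25 + 1/525) = 0.149 at 45%.
- ITT: 1.9 × √(2/525) = 0.117.
- Complier estimate (ITT / p, ignoring the variance of p): 0.117 / 0.30 = 0.39; 0.117 / 0.45 = 0.26.

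**As-treated bias with no treatment effect.** Consenters average d better than non-consenters, and the control arm is a mixture with share p of would-be consenters. The bias is therefore d − p × d = (1 − p) × d. The false-positive rate is P(|Z + bias/SE| > 1.96), before any covariate adjustment.

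| d | Bias, 30% | False positive, 30% | Bias, 45% | False positive, 45% |
|---|---|---|---|---|
| 0.1 | 0.07 | 6.9% | 0.055 | 6.6% |
| 0.2 | 0.14 | 12.8% | 0.11 | 11.5% |
| 0.3 | 0.21 | 22.9% | 0.165 | 19.8% |
| 0.5 | 0.35 | 52.7% | 0.275 | 45.5% |

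A simulation of 8,000 trials per setting at d = 0.3 gave as-treated rejection rates of 23.7% and 20.1%. The complier estimate centred on zero, with rejection rates of 4.9% and 5.4%. With a true complier effect of 0.5, the as-treated mean was 0.71 or 0.67 and the complier estimate averaged 0.50.

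**Precision and power of the complier estimate.** The 95% half-width is 1.96 × SE = 0.77 (30%) or 0.51 (45%). Power for a complier effect of 0.5 is about 25% or 48%, the same as for the ITT test.

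**Exclusion restriction.** If the mailing alone improves non-consenters by m, ITT / p overstates the complier effect by m × (1 − p) / p:
- m = 0.02: 0.05 (30%) or 0.02 (45%)
- m = 0.05: 0.12 or 0.06
- m = 0.10: 0.23 or 0.12

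This is smaller than the as-treated bias when m × (1 − p) / p < (1 − p) × d, that is, when m < p × d. At d = 0.3 the limit for m is 0.09 (30%) or 0.135 (45%). At d = 0.1 it is only 0.03 or 0.045.

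**The case against.** The strongest reply is that the plan already contains the problem. ITT is the set for the primary and secondary objectives, self-selection is the stated reason, and the as-treated work is kept out of every primary analysis. That stands, and it limits the weight of this point. It does not make the as-treated estimate itself any less exposed.

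The size rests on d, which is unknown. That also stands: the false-positive rate runs from near nominal to severe, and no single value should be quoted as the rate. Because the outcome is a change, stable differences in level between consenters and others cancel; d refers only to differences in change. Measured covariates could remove part of it.

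The complier estimate also has a weak point built into the design, because non-consenters receive the decision aid and pillbox. If d is small and the mailing works at all, the complier estimate can be the more biased of the two. It is also less precise and no more powerful than ITT, and two-stage least squares does not suit the odds-ratio, count and spending outcomes. These points argue for adding it with a sensitivity range. They do not support substituting it.

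A reader might infer several stronger things that the documents do not support:
- **That the protocol declares the comparison biased.** It calls the bias potential.
- **That the SAP commits to as-treated tests at p<0.05 on all outcomes.** The all-outcomes plan is in protocol 8.1, the p<0.05 convention is a general rule in SAP 4.1, and SAP 4.2.1 lists no as-treated test. The rates above show what applying that convention would do.
- **That the result will be presented as the effect of the intervention.** Nothing in either document says so.

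**Conclusion.** The point holds as a cheap improvement to an exploratory secondary analysis. It is not a fault in the primary plan, and the primary ITT conclusion is unaffected.

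For assumed d of 0.1 to 0.5, the null bias is 0.07 to 0.35 HbA1c points at 30% uptake and 0.055 to 0.275 at 45%. The corresponding false-positive rates are about 7% to 53% and 7% to 46%. These figures assume SD 1.9, 525 evaluable patients per arm (a completers' approximation, since the SAP plans multiple imputation) and no covariate adjustment. If d has the opposite sign, the null bias reverses and the two-sided rates are the same.

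A complier estimate removes this component because it rescales the randomised contrast. It needs one-sided non-compliance, which the documents support, and the exclusion restriction, which the mailing strains. It also inherits the ITT assumptions about missing HbA1c values.

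**What to change.** In SAP 2.1 and 4.2.1:
1. Add a complier average causal effect for change in HbA1c and for mean PDC, reported beside ITT and ahead of the as-treated result. Use two-stage least squares with random assignment as instrument and the baseline value of the outcome as covariate.
2. Fix one exposure definition, receipt or agreement, and use it for both the uptake rate and the as-treated set.
3. Present the result as an estimate with its confidence interval, not as a further test.
4. State the exclusion restriction, and show how the estimate moves over a range of assumed effects of the mailed decision aid and pillbox, using m × (1 − p) / p.
5. If the as-treated comparison is kept, specify its model and label its results as subject to selection bias, including for outcomes where no complier estimate is given.

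The cost is SAP wording and one extra model for each of the two outcomes. No new data are needed: the as-treated set already requires uptake status, and SAP 3.4 provides for call data. SAP 2.2 places the sharing of full data after the late March 2018 lock, so as the SAP is written the change could precede sight of the outcome data. The downside is the wider interval (SE about 0.39 or 0.26, against 0.17 or 0.15), with no power beyond ITT.
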